4.5.2.7 Mandatory Blood Samples for Biomarker Analysis

During screening phase blood samples will also be collected for storage at the Lombardi Biorepository. These are research samples.

Group A: In Group A there will be 3 time points for research blood collection.

1. The first research blood samples will be collected after consenting and prior to palbociclib treatment.
2. The second research blood sample will be collected after end of palbociclib and prior to surgery, typically on the date of surgery.
3. The third research blood sample will be collected after surgery (End of treatment visit).

Group B: In Group B there will be 2 time points for research blood collection.

1. The pre-operative research blood sample can be collected any time after consenting and prior to surgery in Group B.
2. The second research blood sample will be collected after surgery (End of treatment visit).

Appendix M contains the **Research Blood Sample Form**, to be filled on the day of sample collection and handling until its storage. Samples from this project will be stored at the [name] Lab.

4.5.3 Treatment phase

During this phase, patients enrolled to treatment Group A will receive IP treatment (palbociclib). Treatment Phase for patients on Group A can start as soon as patient successfully completes screening and has the definitive date for surgery determined by the surgeon. Palbociclib starting date will be

defined by date of definitive surgery. The time period for this phase will be 14 to 16 days. This period starts on the date of dose #1 of Palbociclib. Palbociclib treatment is to be given for 12 days.

Patients enrolled to Group B will receive no treatment prior to surgery.

4.5.4 Pre-Surgery phase

For patients enrolled to **Group A**, on Day 13 +/-1 there will be a pre-operative clinic visit, when tolerance to therapy will be assessed, including physical examination/vital signs, ECOG performance status assessment, adverse events, serious adverse events, IP accountability, concomitant medications, measurements of treatment adherence. Laboratory tests will include CBC, CMP and an additional blood sample for research (please refer to item **4.5.2.7 Mandatory Blood Samples for Biomarker Analysis**). After this visit, patients will proceed to scheduled definitive surgery for DCIS. Treatment phase ends on the day of surgery (Day 15 +/-1).

For patients enrolled to **Group B** the pre-surgery experimental phase will only involve Laboratory tests including CBC, CMP and an additional blood sample for research (please refer to item **4.5.2.7 Mandatory Blood Samples for Biomarker Analysis**).

4.5.5 Surgery

On the scheduled day for surgery patient will follow surgery team's recommendations for hospital registration, OR procedures and subsequent discharge home. Surgery will occur on study day 15 +/-1. Research tumor sample will be collected under the supervision of certified pathologist (Tumor Sample #2). The research tumor sample will be transported to [name] Lab where it will be processed and stored for testing. The surgery must happen at the study participating center.

4.5.6 Follow up phases – End of Study Visit and Long Term Follow Up

Follow-Up Phase starts on post operative day #1. The End of Study Visit (EOV) occurs on treatment day 32 +/- 8, which represents a time point situated approximately at 2 to 3 weeks after surgery. On that date, there will be a clinic visit with physical examination/vital signs, ECOG performance status assessment, adverse events, serious adverse events, current medications, and final pathology report. Additional treatments may be required after definitive surgery. Patient will discuss any additional treatments with the primary or treating medical oncologist. Laboratory tests will include CBC, CMP and an additional blood sample for research. A Long Term Follow up (LTF) assessment may be done at year 1 (+/- 30 days) and at year 5 (+/- 60 days) from treatment. The LTF assessment may comprise of Electronic Medical Record Review for clinical data and survival status as well as of a telephone call.

4.6 Patient and Study Discontinuation

Patients who are non-compliant or discontinue Study Treatment will be substituted. Withdrawal of consent for all study participation will end patient activity in the study, translational research and clinical follow up.

5. ASSESSMENT OF SAFETY

5.1 Safety Plan

Palbociclib is currently approved in the US for metastatic breast cancer and is currently in clinical development on other indications. The toxicity is considered predictable based on significant experience with palbociclib on phase I, II and III clinical trials, expanded access, and standard of care use.

5.1.1 Dose Delays and Modifications for Palbociclib

Palbociclib will be used at a lower dose of 100mg PO daily for 12 consecutive days. There will be no dose delays or dose reductions in this trial.

Every effort should be made to administer study treatment on the planned dose and schedule. However, in the event of significant treatment-related toxicity, administration of palbociclib will be discontinued. Patients who discontinue study treatment (i.e. palbociclib for Group A) will continue to be followed according to post treatment follow up as defined in Schedule of Study Procedures (Appendix A).

5.1.2 Treatment discontinuation

Incidence, nature, and severity of adverse events triggering study treatment discontinuation are to be assessed by the investigator and graded according to National Cancer Institute Common Terminology Criteria for Adverse Events, version 4.0 (NCI CTCAE, v4.0), with respective attribution.

Any grade 3 or higher toxicity will trigger treatment discontinuation. In case of concurrent occurrence of > 3x ULN ALT and 2x ULN Total Bilirubin, at any time during the trial, palbociclib will be permanently discontinued.

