4.3.1.4 Dispensation of Palbociclib

The dedicated pharmacist at each site will also be responsible for dispensing the drug to the treatment group patients, as per standard operating practices. Investigator will fill out the *Investigational Drug Order Form (Appendix I)* ordering Palbociclib for a patient. The coordinator will present the filled order form to the Pharmacist so that Palbociclib can be dispensed.

Study pharmacist will dispense 12 capsules for each participant enrolled to Cohort A (treatment cohort).

The patient number should be recorded on the bottle label in the spaces provided by site personnel at the time of assignment to patient. Site personnel must ensure that patients clearly understand the directions for self-medication. Patients should be given a sufficient supply to last until their next study visit and should further be instructed to keep their medication in the bottles provided and not transfer it to any other container. No other medicines should be added to palbociclib bottle.

Due to possible unknown hazards associated with topical and environmental exposure to experimental agents, capsules must not be opened and/or emptied into any vehicle for oral ingestion; capsules must be swallowed intact.

To ensure adequate records and patient compliance monitoring, palbociclib capsules will be accounted for by the site as instructed by the respective study Sponsor and following MGUH standard operational procedures. Hence, the study site pharmacy will maintain a careful record of the inventory and disposition of the agent. Accurate records of all investigational product received at, dispensed to, returned from, returned to, and disposed of by the study site should be recorded. Patients will be instructed to return previously dispensed bottles (including unused drug and/or empty bottles) as well as their completed Palbociclib Diary to the clinic at the pre-operative visit for accountability purposes

([Appendix J](#)). Unused returned medication MUST NOT be re-dispensed to patients. The number of remaining capsules/tablets will be documented and recorded within the eCRF.

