4.3.2 Dosage, Administration, and Compliance

4.3.2.1 Group A

Patients enrolled to **Group A** will receive a 12-day course of Palbociclib before surgery. They will receive Palbociclib 100mg PO daily x 12 days. When definitive surgery date is defined and Operation Room scheduled, day 1 of palbociclib will be determined and Palbociclib dispensed. Administration is performed on an outpatient, self-administration basis. [Appendix C](#) has a model calendar that can be used when planning events based on defined date of surgery.

- Treatment is continuous daily for 12 days, followed by 3 days off [+/- 1 day], followed by definitive DCIS surgery.
- Patients will be encouraged to take their dose of Palbociclib at approximately the same time each day.
- Palbociclib should be taken with food.
- If the patient vomits or misses a dose, an additional dose should not be taken. The next prescribed dose should be taken at the usual time.
- Palbociclib capsules should be swallowed whole (do not chew, crush or open them prior to swallowing).
- Capsules should not be ingested if they are broken, cracked, or otherwise not intact.
- Patients who inadvertently take 1 extra dose during a day must skip the next day's dose.
- If patient takes more than two doses of palbociclib in a day, the patient should bring this to the attention of his or her treating physician.
- Patients should be instructed to record daily administration of the study drug in the Palbociclib Diary ([Appendix J](#)).

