4.3.2.3 Assessment of Compliance with Palbociclib

Study coordinator will meet with patient before surgery and after end of palbociclib treatment and collect empty bottles. At that point the coordinator will document compliance to treatment per protocol.

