4.5 Study Assessments

The study consists of 6 different phases:

1) Pre-Screening Phase	(candidates for study either on Group A or Group B)	
2) Screening Phase	(Group A and Group B)	Study Days -28 to 0
3) Treatment Phase	(Group A only)*	Study Days 1 to 12
4) Pre-Surgery Phase	(Group A only)*	Study Days 12 to 14
5) Surgery	(Group A and Group B)*	Study Days 14 to 16
6) Follow-Up Phase - EOF	(Group A and Group B)	Study Days 25 to 40
Follow-Up Phase - LTF	(Group A and Group B)	EMR review 1yr and 5yr

* Please refer to item **3.1.1 Overview of Study Design, timing of surgery**, for additional details on definitive surgery timing after enrollment for patients on Group B

See **Appendix A Study Procedures** and **Appendix B Study Schema** for details as to how these phases correspond with the Schedule of Assessments calendar, Pre-Screening Phase, Screening Phase, Treatment Phase, Pre-Surgery Phase, Surgery and Follow-Up Phases End of Study Visit (EOF) and Long Term Follow Up (LTF).

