Appendix A: Study procedures

	Screening Phase		Treatment Phase		Pre-surgery	Surgery	Follow up Phase	
Procedure	Screening	Pre-treatment	Treatment start	Last day of treatment	Pre-surgery	Day of Surgery	End of Treatment visit	Long term follow up
Day	(-28 to -1)	(-28 to 0)	1	12	13 +/-1	15 +/-1	32 (+/- 8 days)	1yr and 5yr
Signed Informed Consent Form(s)	x							
Review of Eligibility Criteria	x	x						
Clinical Visit	x ⁹	x ⁷			x ⁷		x	
Review of breast US, Mammograms and breast MRI if available	x							
Disease status	x	x ⁴			x ⁴		x	x ⁶
CTCAE v. 4.03 review of baseline toxicities		x			x ⁴		x	
Archival tumor tissue specimen or 15 unstained slides	x							
Rb testing archival tissue	x ¹							
Tissue for research at definitive surgery						x ⁵		
CBC/diff/platelets	x ⁸	x ⁴			x ⁴		x	
CMP	x ⁸	x ⁴			x ⁴		x	
Coags (aPTT, INR)	x ⁸							
Serum or urine pregnancy test	x							
Blood sample for research - cells		x ²			x ^{2,4}		x ²	

	Screening Phase		Treatment Phase		Pre-surgery	Surgery	Follow up Phase	
Procedure	Screening	Pre-treatment	Treatment start	Last day of treatment	Pre-surgery	Day of Surgery	End of Treatment visit	Long term follow up
Day	(-28 to -1)	(-28 to 0)	1	12	13 +/-1	15 +/-1	32 (+/- 8 days)	1yr and 5yr
Schedule definitive surgery date		x						
Group A: Start palbociclib			x ³					
Group B: no treatment								
Lumpectomy or mastectomy						x		
Pathologic exam of specimen						x		
EMR review							x	1yr and 5yr
Telephone contact							x	1yr and 5yr

1 Rb testing for all participants at screening. Rb negative configures screen failure.

2 Research blood sample for liquid biopsy and tissue banking (serum/plasma and PBMCs). In Group B, pre-operative sample can be drawn any time after consenting and prior to surgery. For details on these samples please refer to item **4.5.2.7 Mandatory Blood Samples for Biomarker Analysis**

3 Palbociclib 100mg PO daily for 12 days; provided by Pfizer and to be dispensed by MGUH/WHC research pharmacy.

4 Group A only.

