5 Tissue sample #2: Under supervision of the certified pathologist, the sample required for pathologic diagnosis will be collected. Excess tissue will be used for research. Research tumor samples will be collected for H&E and IHC (formalin), CRC cultures (conditionally reprogrammed cell media), isolation of RNA and subsequent expression analysis, and for proteomic or metabolomic analysis (Snap Frozen). Non used tissue will be banked. Handling, processing, storage and testing DCIS sample at definitive surgery by pathologist and at Lombardi Research Lab ([name] LAB)

6 Evaluation of clinical characteristics including disease status by EMR review and telephone contact

[figure not shown]
7 Additional visits will be required for patients enrolled on Group A. These include a visit with Medical Oncology team prior to initiation of palbociclib (pre-Treatment) and another visit after end of palbociclib, prior to surgery (pre-Surgery). These visits are not required for patients enrolled in Group B.

8 Tests must be completed at least 5 days prior to definitive surgery in Group B (untreated)

9 Clinical visit -(28) to (-1) is the routine visit typically with the surgeon to discuss newly diagnosed DCIS and surgical plan, at which point the study may be offered to the patient (Group A and B).

[figure not shown]

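### Nothing is scheduled for Group A between the Day 1 start and the Day 13 +/-1 visit, so scheduled assessments can apply the Grade 3 stopping rule to at most 1 of 12 doses, and normally to none

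*Combined protocol and SAP*

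**What the plan says.** Section 5.1.2 states: "Any grade 3 or higher toxicity will trigger treatment discontinuation". It adds a second trigger, concurrent elevation of ALT and total bilirubin. Section 5.1.1 allows neither delay nor reduction of dose, so stopping is the only dose action available.

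Dosing runs from Day 1 to Day 12. Section 4.3.2.1 says: "Administration is performed on an outpatient, self-administration basis".

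In Appendix A the two treatment-phase columns (Day 1 and Day 12) carry one mark between them, the start of palbociclib. CBC, CMP and clinic visit are blank there. The row headed "CTCAE v. 4.03 review of baseline toxicities" is marked at pre-treatment, pre-surgery and the End of Treatment visit. The telephone row is marked only at the End of Treatment visit and at 1 and 5 years. Section 4.5.3, on the treatment phase, lists no assessment.

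The next scheduled contact is in section 4.5.4: "on Day 13 +/-1 there will be a pre-operative clinic visit, when tolerance to therapy will be assessed". Section 4.5 gives the window as "Study Days 12 to 14". Footnote 7 of Appendix A places this visit after palbociclib has ended, as does section 4.3.2.3: "Study coordinator will meet with patient before surgery and after end of palbociclib treatment and collect empty bottles". Under section 4.3.1.4 patients return bottles "as well as their completed Palbociclib Diary to the clinic at the pre-operative visit for accountability purposes".

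**The concern.** A mandatory stopping rule protects a patient only if someone learns of the toxicity while doses remain to be withheld. Here the first scheduled assessment comes when dosing is over or has one day left. During home dosing the rule depends almost wholly on a patient choosing to call.

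The visible patient-facing material does little to prompt that call. The Appendix J diary tells patients to report vomiting or a missed dose at their next visit, which is the pre-surgery visit. Its only instruction to call immediately concerns running out of capsules. Because the diary is handed back at the pre-surgery visit, comments written in it are first seen then.

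What is at stake is avoidable further dosing in a patient who already meets the stopping criterion, in a population with non-invasive disease awaiting curative surgery. The trial's descriptive conclusions are not at stake.

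**Working it through.** **Inputs**

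- Doses: one capsule daily on Days 1 to 12, so 12 doses (sections 3.1.1 and 4.3.2.1). Section 4.3.1.4 has 12 capsules dispensed. Missed doses are not made up (4.3.2.1), so dosing does not run past Day 12.
- Pre-surgery visit: Day 13 +/-1 (4.5.4). 13 - 1 = 12 and 13 + 1 = 14, which reproduces the Day 12 to 14 window in section 4.5.
- Start of the interval: Day 1. Appendix A marks no Day 1 visit, but the diary says that it and the drug supply are handed over that day, and I take this as a contact.

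**Doses that a scheduled visit can withhold.** For a visit on day v, the doses left are 13 - v if the patient is seen before that day's capsule and 12 - v if seen after it, with a minimum of 0.

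| Visit day | Seen before dose | Seen after dose | Days since Day 1 (v - 1) |
|---|---|---|---|
| 12 | 1 | 0 | 11 |
| 13 | 0 | 0 | 12 |
| 14 | 0 | 0 | 13 |

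The maximum is 1/12 = 8%, and it needs laboratory results at once. On the nominal day it is 0. If footnote 7 is read strictly, with the visit after the end of palbociclib, it is 0 in every case.

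**Effect of one call on day c, with c from 6 to 8.** The longest interval without scheduled contact is max(c - 1, v - c).

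| Call day | v = 12 | v = 13 | v = 14 |
|---|---|---|---|
| 6 | 6 | 7 | 8 |
| 7 | 6 | 6 | 7 |
| 8 | 7 | 7 | 7 |

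The range is 6 to 8 days, against 11 to 13 now.

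**Doses spared if a symptomatic Grade 3 event is present at the call**

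- Same-day stop, call before that day's dose (13 - c): 7, 6, 5. Call after the dose (12 - c): 6, 5, 4. The range is 4 to 7 of 12, or 4/12 = 33% to 7/12 = 58%.
- Stop one day later: 6, 5, 4 or 5, 4, 3. The range is 3 to 6 of 12, or 3/12 = 25% to 6/12 = 50%.

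These are ceilings that apply only if such an event is present. The documents give no rate of symptomatic Grade 3 events at 100 mg over 12 days.

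**The case against.** The strongest reply is that this is a design preference. Section 5.1.2 does not tie the rule to visits; it applies whenever toxicity becomes known. Section 5.3.2 covers spontaneous reports and questioning about adverse events, and section 3.2 lets the investigator stop for unacceptable toxicity. The light schedule also has a rationale. Section 3.4.1 reports that the worst cycle 1 neutropenia at 100 mg was Grade 2. Section 3.4.2 puts the blood-count nadir at Days 15-22 and reports no toxicity-related surgery delay in 8 patients given 125 mg for 10 to 12 days. Under section 5.1.3, neutropenia or platelets below the stated threshold at the pre-surgery visit postpone surgery.

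The absolute benefit is probably small. Table 1 (125 mg plus letrozole) gives Grade 3-4 rates of 4% for fatigue, 4% for diarrhea, 2% for nausea, 1% for decreased appetite and 1% for upper respiratory infection. These sum to 12%, possibly with overlap. Section 1.2.5 gives a median treatment duration above 12 months. Assuming a constant hazard over 365 days, 12 patients x 0.12 x 12/365 is about 0.05 events in the whole of Group A; a tenfold higher early hazard gives about 0.5. A call also misses silent neutropenia and silent ALT/bilirubin elevation, which are the laboratory triggers.

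Most of this stands, and it limits the weight of the point. It does not change the count. Section 5.3.2 gives no time for the questioning. The weekly meetings in section 5.4.7 review data, and no scheduled step produces on-treatment data for them. The evidence in sections 3.4.1 and 3.4.2 concerns blood counts and surgery timing, not symptomatic events such as diarrhea or infection. The research-nurse number in the diary is offered for running out of capsules, so it does not close the gap either.

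**Conclusion.** The concern holds on the visible text. Scheduled assessments can withhold at most 1 of 12 doses (8%) under section 5.1.2, and none on the nominal visit day. The interval without scheduled contact is 11 to 13 days.

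The count rests on Appendix A as printed, with a Day 1 hand-over as the last contact. The consent pages, section 5.4.1 on emergency contacts, the Group A schema in Appendix B and the content of Appendices C and D are not visible. A mid-course contact or call instruction could sit there, so I make no claim about what patients are told in those pages.

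Confidence in the count is high. The expected clinical risk is modest and the study result is not threatened. The point is a cheap improvement to patient safety.

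**What to change.** - Add one coordinator telephone query about adverse events at about Day 6-8 to the Group A treatment-phase part of Appendix A, using the existing telephone row.
- Require an unscheduled CBC and CMP if the patient reports fever, infection, bleeding or jaundice.
- Add to the Appendix J diary a side-effect prompt and an instruction to call at once for such symptoms, worded to match anything already in the consent or contact pages.

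The call will not detect laboratory events without symptoms. Whether to add an on-drug CBC/CMP for that purpose is left to the sponsor.

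The cost is 12 calls, plus one for each substitute under section 4.6, made by the coordinator already provided for in section 4.2.2, and an occasional unscheduled blood test. The paperwork is one mark and a footnote in Appendix A, two diary lines, and IRB approval of the amendment under section 8.6. No extra staff or routine blood draw is needed.

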5.1.3 Management of Specific Adverse Events

5.1.3.1 *Neutropenia*

Absolute neutrophil count (ANC) $\geq 1,500/\text{mm}^3$ is required at baseline for study participation. Patients enrolled on treatment Group A will have a pre-surgery visit at day 13 +/- 1 for clinical and laboratorial evaluation. Surgery will be scheduled to occur on day 15 +/- 1. If pre-operative counts reveal neutropenia, the definitive surgery will be postponed until recovery of neutrophil counts.

5.1.3.2 *Thrombocytopenia*

Platelets $\geq 120,000/\text{mm}^3$ are required at baseline for study participation. Patients enrolled on treatment Group A will have a pre-surgery visit at day 13 +/- 1 for clinical and laboratorial evaluation. Surgery will be scheduled to occur on day 15 +/- 1. If pre-operative counts reveal platelets lower than $80,000/\text{mm}^3$, the definitive surgery will be postponed until recovery of platelet counts.

5.1.4 Pregnancy and Contraception Use

Pregnancy is contraindicated during Palbociclib therapy and for at least 3 weeks after the last dose. Based on findings from animal studies and its mechanism of action, Palbociclib can cause fetal harm when administered to a pregnant woman. There are no available data in pregnant women to inform the drug-associated risk. In animal reproduction studies, administration of palbociclib to pregnant rats and rabbits during organogenesis resulted in embryofetal toxicity at maternal exposures that were ≥ 4 times the human clinical exposure based on AUC. Patients will be advised regarding the potential risk of Palbociclib exposure to a fetus. The estimated background risk of major birth defects and miscarriage for the indicated population is unknown. In the U.S. general population, the estimated background risk of major birth defects and miscarriage in clinically recognized pregnancies is 2–4% and 15–20%, respectively.

